## 2. STUDY DESIGN:

Longitudinal (6 month) intervention trial, simple randomized 1:1 with stratification based on age (8-12 years, 13-17 years), non-blinded, to determine if adding the AQI to asthma action plans (AAP) reduces asthma exacerbations, and improves asthma control and quality of life (Figure 3).

Both groups will receive basic education about the AQI including what the AQI is, where to find it, how to use it, and behavioral recommendations by category. In our practice, discussion of the AQI varies by practitioner and patients. While true routine care is likely absence of discussion of the AQI, this was determined to be inappropriate for this study. First, consenting children to the study would result in some discussion of the AQI and therefore bias any true “routine care”. Second, we did not wish to withhold potentially vital asthma self-management to participants. Therefore, all children in the study will receive AQI

[figure not shown]
education. The routine group will receive written AAP only, and the intervention group will receive AAP + AQI written plan. Additionally, the intervention group will be required to download the app onto their or their parent's smartphone (available both for iPhone or android phones) **or** demonstrate the ability to navigate to the airnow.gov website to obtain the AQI at their location. Participants will be followed at monthly intervals for 6 months.

The goal of the AQI is to familiarize persons to their own sensitivities to air pollution and encourage self-modification as needed for personal symptom control. Additionally, there is a goal to prevent discouraging physical activity as most US persons do not meet current daily recommendations.

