## **11.2 Eligibility and Randomization (Visit 1)**

Once the family and participant have indicated willingness to participate and have scheduled a V1, the research coordinator will notify PI. PI will review medical record (granted permission by Asthma Registry patients and allowable access as part of regular duties) to confirm asthma controller medications. PI will prepare AAP for research coordinators to distribute. In the event of a discrepancy between parental reported controller medication and medical record medication, the PI will reach out (with participant parent permission) to healthcare provider managing asthma to confirm asthma controller medications.

After informed consent has been obtained, participant's will be randomized 1:1 by age group. The RC assign random group at time of intervention. Eligibility for lung function tests and/or NEC will be assessed prior to study procedures. Questionnaires will be administered, height and weight will be obtained, lung function tests will be obtained (if eligible), specimens will be collected (if applicable), and AQI education will be provided. For the intervention group only, the AAP containing the AQI information will be provided. The intervention group will demonstrate ability to navigate to either airnow website or airnow app on smart phone. For the control group, an AAP will be provided (containing no AQI information) Both the participants, parents, and research coordinator will know randomization assignment. V1 should not be done if child participant has been sick with respiratory infection in prior 7 days or currently has respiratory symptoms.

If a participant's spirometry demonstrates an FEV1 <80%, the family and participant's managing asthma healthcare provider will be notified. Per family permission, spirometry will be shared with managing asthma healthcare provider. If a participant's FeNO is above 20ppb, with family permission, FeNO will be shared with managing asthma healthcare provider.

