## STATISTICAL PLAN:

Statistical Analysis: Data will be analyzed using SAS (SAS 9.4, Cary, N.C.). Baseline statistics per treatment group will be obtained. Bivariate analysis of covariates (age, sex, race/ethnicity, asthma severity, phenotype (i.e. atopic), socioeconomic status (SES), exposure to primary or secondary tobacco smoke, FeNO, use of controller medication, etc) between groups will be conducted using student t-test or Wilcoxon rank sum and Fisher's exact or Chi-square (where appropriate and based on distribution). Variables with significant differences between groups ( $P<0.05$ ) will be considered for inclusion in multivariate model selection. The effects of physical activity on the outcomes will be compared between groups. Baseline knowledge and usage of AQI will be assessed. Adherence to AQI will also be assessed and compared between groups, with potential stratification by AQI usage. Additionally, differences in weight and BMI will be assessed to evaluate if adherence to AQI promotes sedentarism and leads to increased weight gain. We will evaluate our outcomes (Aims 2 and 3) in three ways. First, we will evaluate the average difference (overall mean) between groups for our primary outcomes using T test or chi-square (where appropriate). Additionally, we will test the average mean difference between each treatment group by multivariate regression (linear for PAQLQ and ACT or CACT, and/or Poisson or logistic regression for mean asthma exacerbations depending on distribution) to allow for covariate adjustment. Second, we will use paired t-tests (or matched Wilcoxon signed-rank) to evaluate the within group effects (6 month mean – baseline) for each primary outcome. Third, to assess the effects over time in our intervention study (correlated repeat measures data), we anticipate analyzing our primary outcomes by generalized linear mixed models (GLMM). For these models, we will first evaluate the distribution of our primary outcome and determine the most appropriate link (e.g. for severe asthma exacerbations: logistic link if there are overall a high proportion of participants with none, or Poisson link if more consistent with count data). A stepwise approach will be used to build all multivariable models. All final models will include age, sex, race/ethnicity, SES, and tobacco smoke exposure. Additionally, the above outcomes will be stratified by age group (8-12y, 13-17y) to determine if the effects are greater in older children for whom the AQI recommendations may be better self-incorporated into outdoor physical activities, vs the younger group who will likely be more reliant on parental checking and activity modification.

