
Power calculations: Power calculations were conducted using G\*Power 354 and SAS (SAS 9.4, Cary, N.C.) using proc glmpower. For mean difference between treatment groups (routine vs. intervention) with sample size of 20 participants per group, two-tailed test, alpha 0.05, we will have  $\geq 90\%$  power to detect a mean difference of 1.05 between groups for mean asthma exacerbations, ACT and C-CACT, and PAQLQ. Our study will provide  $\geq 80\%$  power to detect a mean difference of 0.91. As the clinical difference for ACT is 2-3 points, we anticipate adequate power to detect a clinical difference. The estimated clinically meaningful difference in PAQLQ is 0.5, and our study may be underpowered to detect this small of difference with this analysis. For comparison within each treatment group, comparing the matched difference (end of study- baseline), using the same assumptions above, we will have  $\geq 90\%$  power to detect a mean difference of 0.76, and  $\geq 80\%$  power to detect a mean difference of 0.66. Therefore, we expect better ability to detect changes in PAQLQ within the groups than between them. For repeat measures, we estimated our power using proc glmpower using F test based on Hotelling-Lawley trace. We estimated a study allocation of 1:1, alpha 0.05, repeated measures at 1, 2, 3, 4, 5 months, lear correlation structure with base correlation 0.85 & decay rate of 1, with an estimated mean difference of 2, standard deviation of 2, which provides a  $\geq 90\%$  power for a treatment group size of 12 for overall mean and n=26 for time\*treatment.

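### Allocation is stratified by age group, but the first-listed between-arm test, which also underlies the between-group power figures, has no stratum term

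*Combined protocol and SAP*

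**What the plan says.** Section 2 (Study Design) describes the trial as "simple randomized 1:1 with stratification based on age (8-12 years, 13-17 years), non-blinded". Section 11.2 (Eligibility and Randomization) confirms that children are "randomized 1:1 by age group". Neither section mentions blocks or a permuted list.

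The Statistical Plan evaluates the outcomes of Aims 2 and 3 in three ways. It opens with the simple comparison: "First, we will evaluate the average difference (overall mean) between groups for our primary outcomes using T test or chi-square (where appropriate". No stratum or covariate term is attached. It then returns to the same contrast: "we will test the average mean difference between each treatment group by multivariate regression", to permit covariate adjustment. Paired within-group tests come second and generalized linear mixed models third. Multivariable models are built stepwise, subject to one rule: "All final models will include age, sex, race/ethnicity, SES, and tobacco smoke exposure". Finally, "the above outcomes will be stratified by age group (8-12y, 13-17y", as a look at whether the effect differs by age. No analysis is designated primary.

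The power paragraph opens with the between-group comparison: "For mean difference between treatment groups (routine vs. intervention) with sample size of 20 participants per group, two-tailed test, alpha 0.05". It gives at least 90% power for a difference of 1.05 and at least 80% for 0.91. Separate figures follow for the paired and repeated-measures analyses.

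**The concern.** A factor used to stratify allocation normally belongs in the analysis. If age group predicts the outcome, a test without it leaves the between-stratum variation in its error term and so has less power than a test that includes it. If the arms end up with different age mixes, the unadjusted estimate also leaves that difference uncorrected.

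There is some reason within the protocol to expect age to matter. Section 2.2 measures asthma control with C-ACT at 8-11 years and ACT from 12, so the instrument changes within a year of the stratum boundary. A pooled unstratified t-test puts any difference between the instruments into its error term.

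At stake is the precision of the simplest between-arm result in a 40-child trial whose power paragraph already concedes that it may be underpowered for quality of life. The models that contain age are heavier: five fixed covariates plus stepwise selection. No planned analysis is just arm plus the factor used in randomisation.

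**Working it through.** **Inputs from the documents.** 20 children per group, two-sided alpha 0.05, differences of 1.05 and 0.91, two age strata. No SD is stated for the between-group calculation.

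**Assumptions.** Total SD 1, inferred because it reproduces the plan's figures; 20 children per stratum; no dropout. R² is the share of outcome variance explained by age group. The documents do not give it, so I use 0, 9%, 16% and 25%. With equal strata, the last three correspond to differences between strata of 2√R² = 0.6, 0.8 and 1.0 SD.

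**Step 1: reproduce the plan.** For an unstratified two-sample t-test, the noncentrality is δ = (d/σ)·√(n/2), with 2n − 2 = 38 df and critical value 2.024.

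- d = 0.91: δ = 0.91 × √10 = 2.878, power 80.1%.
- d = 1.05: δ = 1.05 × √10 = 3.320, power 89.9%.

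Both agree with the stated 80% and 90%, so the between-group figures do rest on the unstratified test. The paired figures reproduce separately from a paired t-test with n = 20 (89.7% at 0.76 and 79.9% at 0.66). The repeated-measures figures use a Hotelling-Lawley F test. Neither set depends on the unstratified test.

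**Step 2: add the stratum, arms balanced within strata.** The residual SD becomes √(1 − R²), with 37 df and critical value 2.026. At d = 0.91:

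- R² 0: δ = 2.878, power 80.0%.
- R² 9%: δ = 2.878/0.954 = 3.017, power 83.6%.
- R² 16%: δ = 2.878/0.917 = 3.140, power 86.4%.
- R² 25%: δ = 2.878/0.866 = 3.323, power 89.9%.

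**Step 3: simulate both tests under both readings of the allocation.** Balanced means exactly 10 children per arm per stratum. Unblocked means a fair coin for each child. I ran 100,000 trials per setting. Where independent runs differed slightly, the range is shown.

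| Allocation | R² | Power at 0.91, unstratified | Power at 0.91, arm + stratum | Type I error, unstratified |
|---|---|---|---|---|
| Balanced | 0 | 80% | 80% | 5.0% |
| Balanced | 9% | 81% | 83% | 4.0% |
| Balanced | 16% | 82% | 86% | 3.2-3.3% |
| Balanced | 25% | 83% | 90% | 2.3-2.4% |
| Unblocked | 0 | 79% | 78% | about 5% |
| Unblocked | 9% | 79% | 81-82% | about 5% |
| Unblocked | 16% | 79% | 84-85% | about 5% |
| Unblocked | 25% | 78-79% | 88% | about 5% |

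The arm + stratum model holds about 5% type I error throughout.

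**Step 4: read the plan's other analyses against this.** The regression and mixed models must include age, so some planned estimates of the same contrast recover this precision. The text does not say whether age is the randomisation stratum or age in years. The analyses by age group give two subgroup results, not one stratum-adjusted overall effect.

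**The case against.** The strongest reply is that the plan already adjusts for age. Straight after the t-test it re-tests the same difference by regression, the mixed models follow, and every final model must include age. This stands. A reader might infer that the plan throws away the precision gained by stratifying. The documents do not support that, because only the first-listed test omits the factor.

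A reader might also infer that the unstratified test has the wrong error rate and intervals that are too wide for this design. That holds only if arms are forced to balance within strata. Section 2 says simple randomisation with stratification, and no blocking is described anywhere. Under unblocked allocation the test keeps about 5%. Even where the level is affected the error is conservative, so false positives are not inflated.

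Nor does all of the trial's power reasoning rest on this test: two of the three sets of power figures do not use it.

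Finally, the size depends on an assumed R². The plan's stated reason for looking at age groups is a possible difference in effect, not age as a strong predictor. With a weak age effect the gain is negligible, and under unblocked allocation with none, adjustment loses about a point. For a 40-child pilot this makes the point modest.

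What remains is that the simple comparison omits the design factor, nothing names a leading analysis, and the form of age in the models is left open.

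**Conclusion.** The point holds in a narrow form. The first-listed between-arm test, and the 1.05 and 0.91 figures built on it, ignore the age strata. Because no analysis is named primary, that less precise test could carry the conclusion.

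On assumed R² values of 9% to 25%, omitting the stratum costs roughly 3 to 7 points of power at 0.91 SD under balanced allocation and roughly 3 to 9 points under unblocked allocation. The power gain therefore survives either reading of the randomisation wording, provided age is prognostic. The conservatism of the unstratified test does not survive both readings.

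These sizes assume SD 1, equal strata and no dropout, and apply to continuous outcomes. For binary outcomes the size depends on the exacerbation risk in each stratum, which the documents do not give.

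**What to change.** In the Statistical Analysis paragraph of the Statistical Plan:

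- Make the simple between-arm comparison a linear model with arm and the age stratum recorded at randomisation (8-12, 13-17).
- For binary outcomes, use a Mantel-Haenszel test stratified by the same factor, or a stratified exact test if cells are sparse.
- Keep the unadjusted t-test or chi-square as descriptive only, and say which between-arm analysis leads.
- State whether age enters the regression and mixed models as the randomisation stratum or in years.

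The power paragraph can keep its between-group figures if it says that they refer to an unadjusted t-test.

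The cost is wording and one degree of freedom, with no extra data. If age turns out not to matter, the price is between zero and about one point of power.

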### 2.1 Hypothesis and Specific Aims

We hypothesize that the addition of the AQI to AAP will (A) reduce asthma exacerbations, and (B) improve symptom control & quality of life in children with asthma. To test these hypotheses, in this study we will pursue the following specific aims:

- Aim 1: To recruit a pilot cohort of 40 children with asthma. For proof of concept, we will recruit 40 children with asthma from Children's Hospital of Pittsburgh, the only children's hospital serving southwest Pennsylvania (metropolitan area >2.6 million people). Baseline knowledge about the AQI including familiarity, usage, and prior healthcare provider discussion will be assessed.

- Aim 2: To evaluate if the addition of the AQI to AAP reduces asthma exacerbations in a pilot study of children. Participating children (Aim 1) will be randomized to one of two groups. All participants/caregivers will receive an AAP and verbal AQI education. The intervention group will additionally demonstrate the ability to check the AQI, and AQI recommendations will be incorporated onto their written AAP. Children will be followed monthly for 6 months to evaluate adherence to AQI recommendations and assess the frequency of asthma exacerbations, defined per ATS guidelines. Other known factors contributing to asthma exacerbations, such as asthma severity, viral illnesses, allergic triggers will also be monitored.
- Aim 3: To examine whether the addition of the AQI to AAP improves asthma symptom control and quality of life in a pilot study of children. Asthma symptom control will be measured in participating children monthly, and quality of life will be assessed before randomization and at 6 months. Symptom control and quality of life will be evaluated within (before/after intervention) and between groups.

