## 2.3 Questionnaires

7 questionnaires will be administered to the parents and children of study participants (see Figure 4). (1) Intake Questionnaire: this is a respiratory/general health questionnaire used by the [REDACTED] Study. (2) Tobacco Questionnaire- this is a short questionnaire from questions used on the National Youth Tobacco Survey. (3) AQI intake & follow up: Intake: there are no existing questionnaires evaluating what parents know about the AQI as pertains to their children with asthma. This questionnaire contains questions from NHANES and BRFSS with modifications. The AQI intake has a section to be completed by the parent to understand the parent's knowledge and practices regarding the AQI. The

intake questionnaire additionally contains a section for the child to complete, which is the AQI follow up questionnaire. The follow up questionnaire was developed by the PI to assess usage of the AQI. **(4)** Asthma Control Test (ACT) and Childhood Asthma Control Test (C-ACT) are validated questionnaires to assess asthma control in the last 4 weeks. **(5)** Pediatric Asthma Quality of Life Questionnaire (PAQLQ(S)) is validated questionnaire that will be interviewer-administered. **(6)** Physical activity questionnaire contains modified questions from NHANES and The Physical Activity Questionnaire for older children and adolescents. **(7)** Shortened respiratory questionnaire (sRHQ): this is a short questionnaire that has been modified from the [REDACTED] study. It is designed to capture asthma exacerbations.

The order of the questionnaires is important. The AQI intake form will be completed by the parent/guardian and the child participant prior to AQI education/intervention.

**2.4 Lung Function Tests:** Spirometry and fractional exhaled nitric oxide (FeNO) will be obtained at entrance and exit visit as secondary measures of control (e.g. forced vital capacity (FVC), forced expiratory volume in 1 sec (FEV1), and FEV1/FVC).

**2.5 Anthropometric measures:** Height and weight will be obtained at the baseline and exit visit, to assess if adherence to AQI potentially alters weight/BMI by increased sedentarism.

**2.6 Urine collection:** as an ancillary to this study, will collect urine for cotinine measurement (nicotine metabolites) and store.

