## 8. RISKS AND DISCOMFORTS:

### 8.1. Procedures

**Figure 5: Back of AAP + AQI**

**Asthma checklist before going outside:**

- ALWAYS** keep your rescue inhaler (& spacer) handy
- Check the air quality index (AQI):  
airnow.gov **OR** Airnow smartphone app
- Watch for symptoms: cough, wheezing, difficulty breathing, chest tightness.
- If you have symptoms, this is a sign to take it easy. Follow your yellow zone & consider: limiting time outside, increasing the number of breaks, do less intense activities, stop activity, or go indoors.

AQI	AQI #	What to do:
Good	0-50	No action required. A good day to be active outside!
Moderate	51-100	Children who are unusually sensitive to air pollution could have symptoms. If so, take steps to reduce prolonged or heavy exertion.
Unhealthy for sensitive groups	101-150	Ok to be active outside for short activities. For longer activities take more breaks & do less intense activities. Reduce prolonged or heavy outdoor exertion.
Unhealthy	151-200	Move longer or more intense activities indoors. Avoid prolonged or heavy exertion outdoors- a good day to work out in the gym.
Very Unhealthy	201-300	Move activities indoors. Avoid all physical activity outdoors.
Hazardous	301-500	Stay indoors and keep activity levels low. Keep windows closed and avoid frying/broiling on these days.

- Air pollution can make asthma symptoms worse and trigger attacks. Asthma symptoms can happen even on days when the air quality is good. Always keep your rescue inhaler handy.
- Exercising on days when air pollution is bad can mean more air pollution in your lungs. Changing your activity level can help. For example, take a walk instead of a run. Changing how long you spend outside exercising can also help. For example, don't stay outside as long.

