**Plan activities when and where pollution is lower:**

- Ozone is usually higher on hot summer days in the afternoon & early evening. On days ozone is high, plan your outdoor activities in the morning.
- Particulate pollution can be higher in certain places. Try to avoid exercising where particles are higher. Examples: near busy roadways, during rush-hour traffic, near industrial areas, and when there is smoke in the air.

*Don't let asthma keep you from being active. The CDC recommends 60 minutes of physical activity a day. If asthma is limiting your activity, talk to your doctor!*

Table 1: Study Procedures

VISIT	LOCATION	QUESTIONNAIRE	EMR	MEASURES	SPECIMENS
1	In-person, PCTRC	Intake, AQI intake, PA, ACT or CACT, PAQLQ, tobacco intake	Confirm asthma controller medications, IgE, allergen testing, eosinophils, BAL or sputum eosinophils	Spirometry, FeNO, height, weight	Nasal epithelial cells, urine
2	Telephone	sRQ, AQI_f/u, PA, ACT or CACT.	-	-	-
3	Telephone	sRQ, AQI_f/u, PA, ACT or CACT.,	-	-	-
4	Telephone	sRQ, AQI_f/u, PA, ACT or CACT.	-	-	-
5	Telephone	sRQ, AQI_f/u, PA, ACT or CACT.	-	-	-
6	Telephone	sRQ, AQI_f/u, PA, ACT or CACT.	-	-	-
7	In-person, PCTRC	sRQ, AQI_f/u, PA, ACT or CACT.	-	Spirometry, FeNO, height, weight	Nasal epithelial cells, urine

Intake questionnaire (completed by parent); AQI intake- includes parent portion (completed by parent) + AQI follow up (completed by participant); PA=physical activity (parent and/or participant), ACT=asthma control test ages 12 and older (completed by participant); CACT=childhood asthma control test for ages 8-11 (completed by parent and participant); PAQLQ(s)-pediatric asthma quality of life questionnaire (completed by participant); participant tobacco intake form (completed by participant); sRQ= shortened respiratory questionnaire (completed by parent); AQI\_f/u=AQI follow up questionnaire (completed by participant).

**8.1a Questionnaires:** the risks from questionnaire administration involves social-psychological risk resulting from inadvertent disclosure of medical information and/or questions may create discomfort. Participants and parents do not have to answer any question that they do not wish to answer.

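### Ambient AQI and season are neither linked to follow-up nor modelled, so adherence to the card's AQI advice has no planned denominator and the before/after tests mix season with effect

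*Combined protocol and SAP*

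**What the plan says.** - **Purpose.** Section 2.1, Aim 2: "Children will be followed monthly for 6 months to evaluate adherence to AQI recommendations and assess the frequency of asthma exacerbations". It also says severity, viral illness and allergic triggers will be monitored. Air quality and season are not named.
- **Card (Figure 5).** At AQI 0-50: "No action required. A good day to be active outside". At 51-100: "Children who are unusually sensitive to air pollution could have symptoms. If so, take steps to reduce prolonged or heavy exertion". At 101-150, the first band with a change for every child: "For longer activities take more breaks & do less intense activities. Reduce prolonged or heavy outdoor exertion". Higher bands are stricter. Some advice holds at any AQI, for example "If you have symptoms, this is a sign to take it easy". On timing, the card says "Ozone is usually higher on hot summer days in the afternoon & early evening".
- **Measurement.** Section 2.3: "The follow up questionnaire was developed by the PI to assess usage of the AQI". Tables 1 and 2 list questionnaires, record review, spirometry, FeNO, height, weight and specimens. Neither lists ambient AQI, pollutant level or season.
- **Analysis.** Statistical Plan: "All final models will include age, sex, race/ethnicity, SES, and tobacco smoke exposure". Adherence is to be compared between groups, possibly stratified by AQI usage, but is not defined. Paired tests assess change within each group, and mixed models assess effects over time. The covariate list is open-ended, but no AQI, season or calendar term is named anywhere.
- **Power.** The Power calculations expect changes in PAQLQ to be easier to detect within groups than between them.

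**The concern.** The part of the intervention that distinguishes one AQI level from another operates only on days when the AQI is raised. Children are followed for 24 weeks each, and no enrolment season or window is stated, so they may meet very different numbers of such days. Three things follow.

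1. **Adherence.** Checking the AQI is not the same as acting when the card advises it. A child who changed nothing because no day exceeded 100 cannot be told from one who disregarded many such days unless the days are counted.
2. **Before/after tests.** V7 falls nearly half a year after V1. A within-arm change therefore contains any seasonal shift in control or exacerbations, and randomisation does not protect a comparison made inside one arm.
3. **Describing a null, and planning the next trial.** A pilot should report how often the graded advice applied. As planned, this one would not.

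**Working it through.** **1. The plan's own power figure.** Inputs (Power calculations): 20 per group, two-sided alpha 0.05. The SD is not stated; the figures reproduce with SD = 1. The two-sample t-test (noncentral t, noncentrality d × √(20/2)) gives 89.9% at d = 1.05 and 80.1% at d = 0.91, against the stated ≥90% and ≥80%. The paired t-test (noncentrality d × √20) gives 89.7% at 0.76 and 79.9% at 0.66. All four agree to rounding.

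None allows for how often the AQI is raised. As an illustration, if only a share s of the 1.05 SD effect can arise, between-group power is 68% (s = 0.75), 37% (s = 0.5) or 13% (s = 0.25). The true share cannot be obtained from the documents.

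**2. The missing denominator.** Follow-up is 24 × 7 = 168 days. Assume a share p of days is raised and that days are independent.

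| p (assumed) | Raised days, 168p | No raised day in a 28-day interval, (1−p)^28 |
|---|---|---|
| 1% | 1.7 | 75% |
| 2% | 3.4 | 57% |
| 5% | 8.4 | 24% |
| 10% | 16.8 | 5% |

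Over this range, a monthly report of no change in activity can mean anything from nothing to act on to advice ignored.

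**3. What days above 100 could contribute.** With share f of days above 100 and risk ratio 1.5 on them (both assumed), the preventable share is f(RR−1)/[1+f(RR−1)]:

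- f = 2%: 0.010/1.010 = 1.0%
- f = 5%: 0.025/1.025 = 2.4%
- f = 10%: 0.050/1.050 = 4.8%
- f = 30%: 0.150/1.150 = 13.0%

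This covers days above 100 only. It is not a ceiling on the card's whole effect.

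**4. Season between arms.** Assume start dates uniform over 52 weeks, 24 weeks of follow-up and one 13-week season. Let W be a child's weeks in that season.

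- P(W = 0) = (52−24−13)/52 = 29%; P(W = 13) = (24−13)/52 = 21%.
- Mean W = 24 × 13/52 = 6.0.
- E[W²] = 169 × 11/52 + 2 × (13³/3)/52 = 35.75 + 28.17 = 63.92, so Var(W) = 63.92 − 36 = 27.9 and SD = 5.3 weeks.
- SD of the arm difference in mean W = 5.28 × √(2/20) = 1.67 weeks. A difference of 2 weeks or more occurs in 23% of trials.

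In outcome terms, suppose the season doubles the weekly rate λ. The mean count per child is λ(24+6) = 30λ, and season adds variance λ² × 27.9.

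- Mean 1 event: 27.9/900 = 0.031 on a Poisson variance of 1, about 3%.
- Mean 2 events: 4 × 27.9/900 = 0.124 on a variance of 2, about 6%.

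**5. Season within arms.** Suppose an outcome follows a yearly sine wave of amplitude A (assumed). Two readings 24 weeks apart can differ by up to 2A × sin(π × 24/52) = 2A × 0.993, almost the full peak-to-trough swing. If starts are spread evenly over the year this averages to zero and adds only noise. If enrolment clusters, it shifts the mean change. The plan fixes neither.

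**The case against.** The strongest reply has five parts.

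- **The card is not only AQI-triggered.** Keeping the inhaler handy, checking the AQI, watching for symptoms and choosing time and place apply on any day. This stands. A reader might infer that a child with no day above 100 had nothing to follow; the card contradicts that.
- **Adherence is not ignored.** AQI follow-up and physical activity forms are completed at V2 to V7, and the documents do not show their items, which may ask about action on bad-air days. This stands against any inference that adherence cannot be judged at all. It does not supply the number of days on which action was advised.
- **The data can be recovered.** Visits are scheduled at 4-week intervals at one site, children planning to leave the area are excluded, and the AQI is public. This stands. The gap is one of pre-specification, but linkage added after results are seen would be post hoc.
- **Randomisation balances season and AQI in expectation.** This stands for the between-arm comparison, and the precision loss is small. It does not help the within-arm tests.
- **A null would be hard to read anyway,** with 40 children and AQI education in both arms. This also stands. A null would still answer whether the printed card and demonstration helped under the conditions that occurred, so the documents do not support calling it uninterpretable.

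**Conclusion.** The point holds as a gap in planning that is cheap to close. Aim 2's adherence has no planned denominator, the within-group V1-to-V7 tests are confounded with season, and a null could not be described by how often the graded advice applied. The between-arm comparison is not biased in expectation.

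The size is uncertain because the documents give no AQI frequencies, exacerbation rate or enrolment window. On assumed shares of 1% to 10%, a child has about 2 to 17 raised days. The gain in precision from modelling season is modest: about 3-6% of the variance of the arm difference, assuming one 13-week season doubles the rate and children have 1 to 2 events each. The main gain is in what the adherence and before/after results can support.

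A reader might go further and want a null with few raised days reported as the intervention not having been triggered. The documents do not support that: the card also acts at other AQI levels, and without a preset threshold the label could excuse any negative result. Nor do they support counting adherence only above 100, since the 51-100 band carries advice and Section 2 gives learning one's own sensitivity as a goal.

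**What to change.** 1. **Link exposure.** Attach publicly available daily area AQI and calendar dates to each child's 4-week intervals. Report days at 51-100, 101-150 and above 150 by arm.
2. **Define adherence.** Report action taken relative to the days on which the card called for it, alongside usage. Include the 51-100 band, noting that advice there depends on the child's symptoms, so its day count is an upper limit on action days.
3. **Model season.** Add a calendar-season term to the mixed models for exacerbations and ACT/C-ACT. State that unadjusted within-group V1-to-V7 changes, including PAQLQ, will not be read as intervention effects.
4. **Keep the rest exploratory.** Present raised-AQI days and their interaction with arm as exploratory only, with a confidence interval.

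Cost: protocol and SAP wording, one small data pull and a few extra model parameters. No extra visits or participants are needed. The 40 × 6 = 240 child-intervals come from only 40 children, the power section assumes a base correlation of 0.85, and five covariates are already forced into every final model. The interaction will therefore be imprecise.
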